8.3 Statistical or Analytic Methods

Describe the statistical methods (or non-statistical methods of analysis) that will be employed.

Aim 1

All data will initially be assessed with descriptive techniques to determine distributions and identify outliers. Baseline to post-intervention changes in participants' CMAI, NPI-NH, and ARS scores will be used as the outcomes in all subsequent analyses. To conduct the group analysis, each participant will serve as their own control, which allows minimal use of control variables. The effect of the intervention will be analyzed using multi-level modeling to adjust for clustering of participants at the facility level. We will use the daytime and nighttime average of lighting dosages (lux and CS) from the personal light monitors as the independent variable to analyze the effect of SABL on changes in CMAI, NPI, and ARS. Although not powered for a detailed analysis, we will explore the impact of participant characteristics (sex, age, race, ethnicity, ADRD stage, and daylight exposure) on the intervention effect by adding them as covariates to the regression model.

Aim 2

All data will initially be assessed using descriptive techniques to examine underlying assumptions and detect any violations. To assess the intervention fidelity, the lux and CS data measured via manual measurements will be analyzed using one sample t-tests to analyze lighting levels during the day and nighttime, compared to the target levels. The data from personal light monitors will be analyzed similarly at individual level. Although not powered for a detailed analysis, we will explore the impact of participant characteristics (e.g., sex, age, race, dementia stage, comorbidity, facility, and daylight conditions) on the lighting received based on the personal light monitor.

Aim 3

Quantitative Analysis: The data include ratings of acceptability, feasibility, appropriateness, time, and cost of installing and maintaining the intervention. All data will be analyzed using descriptive analyses. Although not powered for a detailed analysis, we will explore differences in perceptions of intervention feasibility and acceptability between sexes as well as the difference across professional roles and between facilities.

Qualitative Analysis: The data include statements about SABL's acceptability, feasibility, and appropriateness by NH employees. All interviews will be analyzed to identify patterns of feedback in implementation outcomes. We will use the five phases of thematic analysis in an iterative process: 1) transcripts and field notes will be read and reread, 2) building on the notes and ideas generated, the analysis will be coded, 3) identifying themes or patterns in the data that are relevant to the research question, 4) naming and defining each theme, 5) extracting analytic narrative and exemplar data to illustrate the themes. This approach will reveal themes related to the acceptability, feasibility, and appropriateness of the intervention.

Mixed Methods Analysis: After quantitative and qualitative data are analyzed, the data will be merged by PI [name] and Co-I [name], using the spiraled analysis to compare and contrast the results. The data will be evaluated for convergence, divergence, relationships, contradictions, and new findings. Merged results will be reported in a joint display.

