1.0 Objectives

1.1 Study Objectives

Describe the purpose, specific aims or objectives. State the hypotheses to be tested.

Aim 1: Pilot test the effect of Smart Ambient Bright Light (SABL) in reducing agitation in persons with dementia. We will also examine the effect of SABL on other Behavioral and Psychological Symptoms of Dementia (BPSD), affect, and sleep and side effects. We hypothesize that participants will show less agitation and other BPSD and improve affect and sleep during and after SABL compared to baseline and control periods. We will also explore the intervention effect on residents' other behavioral and psychological symptoms and affect and monitor potential side effects.

Aim 2: Evaluate the fidelity of the SABL delivery. We will evaluate the fidelity of SABL delivery. We will measure lighting intensity (lux) and circadian stimulus (CS) levels via two methods: 1) on-site light measurements, and 2) a personal light monitor. We will compare the actual lighting dosage to our target lighting dosage.

Aim 3: Evaluate the feasibility of implementing the SABL. We will use convergent mixed methods to evaluate the acceptability, feasibility, and appropriateness of the interventions from perspectives of nursing home staff and administrators.

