3.3.2 Follow-up for withdrawn subjects

Describe when and how to withdraw subjects from the study; the type and timing of the data to be collected for withdrawal of subjects; whether and how subjects are to be replaced; the follow-up for subjects withdrawn from investigational treatment.

We will collect information about reasons for withdrawal upon the timing of withdraw.

Aims 1 and 2: Residents:

If any residents who did not complete the procedures of the study may be replaced with a new participant. We aim to replace the participant with a resident from the same facility, if possible. All the data collected from the participants prior to the withdrawal may be included for analysis. The new participants will go through the entire 13-week study procedures from baseline through post intervention.

Aim 3: Staff and administrators

Aim 3: Any participants who did not complete the study procedures may be replaced with a new staff or administrators with a similar role/position at the facility. All the data collected from the participants prior to the withdrawal may be included for analysis.

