We will assess residents' cognitive impairment using the Montreal Cognitive Assessment (MoCA). A score of ≤ 22 on the Montreal Cognitive Assessment (MoCA) is considered cognitive impairment and eligible for this research study. We will assess residents' agitation symptoms using the Cohen-Mansfield Agitation Inventory (CMAI), based on the residents' behaviors over the past week. A CMAI score of ≥ 45 is considered presence of agitation and is eligible for this study. Residents who have cognitive impairment (MoCA score ≤ 22) and agitation (CMAI score ≥ 45) are considered eligible and will be enrolled for the study.

Aim 3: Staff and administrators

The screening for staff and administrators will be conducted after consent has been provided. Our inclusion criteria are as below: a) nursing home employed healthcare workers employed for ≥ 3 months, b) age ≥ 18 , and c) English speaking. We will provide the inclusion criteria to the staff during the recruitment meeting and, if they are potentially eligible and interested in participating, the research team will ask them to provide their contact information. Next the research team will reach out to them individually to obtain consent.

In some studies, these procedures may not take place unless HIPAA Authorization is obtained OR a waiver of HIPAA Authorization when applicable for the screening procedures is approved by the IRB.

*Unless informed consent is waived by the IRB, screening before consent is only permitted when screening activities are limited to the collection of information through oral or written communication OR when identifiable private information or identifiable biospecimens is obtained by accessing records or stored identifiable biospecimens. Screening before consent is not permitted if data will be used for activities other than eligibility screening/recruitment (e.g., data analysis).

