7.1 Study Design

Describe and explain the study design.

Aim 1: Pilot test the effect of SABL in reducing agitation in persons with dementia. This is a crossover, cluster randomized control trial to pilot test the effect of SABL in NHs. This design includes a 4-week intervention period and 2-week washout period. This design will allow for participants to act as their own control and thus reduce the needed sample size and strengthen the research rigor. The study procedures include five phases over 13 weeks. We will recruit a total sample of 40 nursing home residents with dementia and agitation from the 2 nursing homes, 20 residents from each nursing home. The two NHs will be randomly assigned into different sequences for intervention and control. Otherwise, the same study procedures will be

conducted simultaneously at the two NHs. During the daytime, participants will be guided and encouraged to spend time in the designated areas in the dining room and activity room for their meals and daily activities. For blinding prior to control period, we will perform installation procedures with non-SABL light bulbs. We will evaluate the effect of SABL on agitation, other BPSD, affect, and sleep, based on the actual lighting levels participants receive measured by personal light monitors. The study procedures include five phases: 1) baseline, 2) intervention, 3) post intervention/washout, 4) control, and 5) post control/washout. The sequence of intervention and control differs between the two NHs based on randomized assignment. Agitation and lighting will be measured at baseline and then once every two weeks throughout the study. We hypothesize that participants will show less agitation during and after SABL compared to baseline and control periods. We will also explore the intervention effect on other BPSD and affect and monitor adverse effects. **Aim 2: Evaluate the fidelity of the SABL delivery.** We will evaluate the fidelity of SABL delivery by measuring lighting intensity (lux) and CS levels in two ways: 1) on-site light measurements, and 2) a personal light monitor. The actual lighting data will be compared to the intended SABL design.

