8.0 Number of Subjects and Statistical Plan

8.1

Number of Subjects

Indicate the maximum number of subjects to be accrued/enrolled, to include all persons who sign consent for the study. If applicable, distinguish between the number of subjects who are expected to be enrolled and screened, and the number of subjects needed to complete the research procedures (i.e., numbers of subjects excluding screen failures.)

Aims 1 and 2: Residents

Resident: The target sample size is 40 nursing home residents. We expect to screen 80 potential residents to identify and enroll 40 eligible residents.

Aim 3: Staff and Administrators

Staff: We plan to enroll 16 NH staff/administrators, including three CNAs, one activity staff, one nurse, one DON, one DOM, and one NHA.

8.2

Sample Size Determination

If applicable, provide a justification of the sample size outlined in section 8.1 to include reflections on, or calculations of, the power of the study.

Aims 1 and 2: Residents

We will recruit 40 residents with ADRD and agitation, 20 from each NH. The two NHs have at least a floor or a wing that is primarily dedicated to residents with ADRD, where we plan to

install the lighting and carry out the study. As attrition is expected to be around 10%, based on prior studies with a similar population, this will result in a final sample size of 36. This sample size was calculated based on a significance level of $\alpha=.05$, medium effect size Cohen's $d=0.53$, reported in previous studies, power=0.92.

Aim 3: Staff and Administrators

CNAs, activity staff, and nurses provide the most direct care. Priority will be given to individuals who provide care for resident participants. DONs, DOMs, and NHAs are decision makers for intervention implementation. The DOMs can provide feedback on the feasibility of installing and maintaining the lighting system and ensure the installation follows NH regulations.

Potential participants will be initially identified by NH staff and confirmed by the research team. Sample size may be increased to reach data saturation.

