Study Title: The Effect of Smart Ambient Bright Light for Nursing Home Residents with Alzheimer's Disease and Related Dementias (Smart Lighting Study)

PIs: [name] (Contact PI) and [name]

NCT05825404

04-24-2023

Data Analysis Plan

Aim 1: Pilot test the effect of SABL in reducing agitation in ADRD.

All data will initially be assessed with descriptive techniques to determine distributions and identify outliers. Baseline to post-intervention changes in participants' CMAI, NPI-NH, and ARS scores will be used as the outcomes in all subsequent analyses. To conduct the group analysis, each participant will serve as their own control, which allows minimal use of control variables. The effect of the intervention will be analyzed using multi-level modeling to adjust for clustering of participants at the facility level. We will use the daytime and nighttime average of lighting dosages (lux and CS) from the personal light monitors as the independent variable to analyze the effect of SABL on changes in CMAI, NPI, and ARS. Although not powered for a detailed analysis, we will explore the impact of participant characteristics (sex, age, race, ethnicity, ADRD stage, and daylight exposure) on the intervention effect by adding them as covariates to the regression model.

Aim 2: Evaluate the fidelity of the SABL delivery.

All data will initially be assessed using descriptive techniques to examine underlying assumptions and detect any violations. To assess the intervention fidelity, the lux and CS data measured via manual measurements will be analyzed using one sample t-tests to analyze lighting levels during the day and nighttime, compared to the target levels. The data from personal light monitors will be analyzed similarly at individual level. Although not powered for a detailed analysis, we will explore the impact of participant characteristics (sex, age, race, ADRD stage, co-morbidity, facility, and daylight conditions) on the lighting received based on the personal light monitor.

Aim 3: Evaluate the feasibility of implementing SABL.

The data includes ratings of acceptability, feasibility, and appropriateness. All data will be analyzed using descriptive analyses.

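### The Aim 1 analysis never specifies the SABL-versus-control comparison that the crossover was built to provide

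*Protocol*

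**What the plan says.** Protocol sections 1.1 and 7.1 both state the hypothesis as less agitation "during and after SABL compared to baseline and control periods". Section 7.1 justifies the crossover on the ground that each resident supplies his or her own comparison, which lowers the sample size needed. It sets out the phases: "The study procedures include five phases: 1) baseline, 2) intervention, 3) post intervention/washout, 4) control, and 5) post control/washout". The two homes are randomised to opposite orders. Section 7.2 and Table 1 schedule the CMAI and the light monitor at weeks 1, 3, 5, 7, 9, 11 and 13, so control-period outcomes are collected.

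For the Aim 1 analysis, section 8.3 says: "Baseline to post-intervention changes in participants' CMAI, NPI-NH, and ARS scores will be used as the outcomes in all subsequent analyses". On the predictor it says: "We will use the daytime and nighttime average of lighting dosages (lux and CS) from the personal light monitors as the independent variable". On the model, the SAP repeats the protocol: "The effect of the intervention will be analyzed using multi-level modeling to adjust for clustering of participants at the facility level". The only other covariates are resident characteristics and daylight exposure, offered as exploratory. Neither document names a term for condition, period, sequence or visit, or a difference between SABL and control. Section 7.4.25 leaves the final modelling approach to diagnostics.

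**The concern.** A crossover earns its efficiency by comparing the same resident under both conditions. If the outcome in every analysis is the change from baseline to after the intervention, the control phase has no stated role and the control half of the hypothesis has no test.

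Two kinds of analysis could follow from the text as written:

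- **A test of mean change** is an uncontrolled before-after comparison. It is open to time trends and, depending on how baseline is measured, to regression to the mean.
- **A slope of change on received dose** is not moved by a shift common to all residents. It does, however, compare residents who received more light with residents who received less. Dose is observed after randomisation, depends on daylight and on where residents spend their time, and is mixed with home and calendar time.

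Neither answers the question that the trial poses.

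**Working it through.** **1. The plan's power figure.** Inputs from section 8.2: d = 0.53, alpha 0.05, power 0.92, 40 enrolled, 36 after 10% attrition (40 × 0.9 = 36). For a paired t-test the noncentrality is d√n.

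- n = 36: 0.53 × 6 = 3.18, giving power 0.930 one-sided and 0.871 two-sided.
- n = 40: 0.53 × 6.325 = 3.35, giving two-sided power 0.905 (t) or 0.918 (normal approximation).
- Parallel comparison, 18 per home: 0.36 two-sided, 0.48 one-sided.

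So 0.92 is a within-resident figure, either one-sided at 36 or two-sided at 40. The same arithmetic fits a before-after change and a SABL-minus-control difference, so it does not supply the missing contrast.

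**2. The calendar.** From section 7.3, 1 + 4 + 2 + 4 + 2 = 13 weeks. Control-period visits are weeks 9 and 11 in NH A and weeks 3 and 5 in NH B.

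| Reading of *post-intervention* | NH A | NH B | Weeks from baseline (A, B) | Control-period scores used |
|---|---|---|---|---|
| Named phase after SABL is removed | week 7 | week 13 | 6, 12 | none |
| Last visit under SABL | week 5 | week 11 | 4, 10 | none |
| End of schedule | week 13 (post control) | week 13 | 12, 12 | none |

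The third reading comes from section 3.3.2: "The new participants will go through the entire 13-week study procedures from baseline through post intervention".

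**3. Scores used.** Scheduled: 36 × 7 = 252. Used in one change score per resident: 36 × 2 = 72. Control-period scores left out: 36 × 2 = 72.

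**4. Time trend (assumed size).** On the first two readings the homes' intervals differ by 6 weeks. A drift of 0.02 to 0.05 SD per week gives 6 × 0.02 = 0.12 to 6 × 0.05 = 0.30 SD between the homes' mean changes with no SABL effect.

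**5. If the mean change were tested (n = 36, two-sided 5%).** With no SABL effect, non-treatment shifts of 0.1, 0.2, 0.3 and 0.4 SD of change give rejection rates of 9%, 21%, 42% and 65%. In 20,000 simulated trials with the shift equal in both periods, a period-adjusted SABL-minus-control test rejected 5.1% at 0.2 SD and 4.9% at 0.4 SD. The before-after test rejected 21.8% and 65.0%.

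**6. Regression to the mean.** This affects a mean change only, and only if the screening CMAI also serves as baseline, which the documents do not settle. Section 4.2.4 sets the entry rule: "A CMAI score of ≥ 45 is considered presence of agitation and is eligible for this study". The expected fall is (1 − ρ) × φ(z)/P(pass), where the last factor is 0.798, 0.424 and 0.195 for 50%, 75% and 90% passing. The 50% figure is the upper end implied by section 8.1, "We expect to screen 80 potential residents to identify and enroll 40 eligible residents", because that ratio covers all eligibility criteria.

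| Passing cut-off | ρ = 0.8 | ρ = 0.7 | ρ = 0.6 |
|---|---|---|---|
| 50% | 0.16 SD | 0.24 SD | 0.32 SD |
| 75% | 0.08 SD | 0.13 SD | 0.17 SD |
| 90% | 0.04 SD | 0.06 SD | 0.08 SD |

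If baseline is a separate later measurement, the fall is zero under equal correlations.

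**7. The dose slope.** Simulation with no true effect: 18 per home, test-retest correlation 0.7, drift as in step 4, a dose gap between homes of 0.5 to 1 SD, no home term, 20,000 runs. The false-positive rate was 0.052 to 0.080, and about 0.05 with a home term.

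**8. The proposed contrast.** On cell means the estimate is ½[(A under SABL − A under control) + (B under SABL − B under control)].

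- With home, visit and condition terms the model is full rank (6 of 6). It recovers a true −0.50 SD exactly under a common drift plus a common fall.
- A 0.20 SD fall confined to NH A in weeks 9 and 11, whether a local event or carryover, moves the estimate to −0.40; the bias is half the shift.
- Adding home-by-period gives rank 6 of 7, so that term cannot be estimated.
- A joint model over the six follow-up visits with SABL and post-SABL terms is full rank (9 of 9).

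**The case against.** The strongest defence is that the text implies the contrast without writing it. It speaks of changes in the plural, says residents are their own controls, uses a multi-level model, and schedules light and outcomes together at every visit. Control weeks could then enter as low-dose records. Received dose is also a deliberate choice, stated in sections 2.3, 7.1 and 7.4.1, in a trial described as a pilot, and section 7.4.25 keeps the model form open.

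Some of this stands. The per-visit dose reading is possible, so the score counts in step 3 describe the literal text and not every conceivable analysis. The drift and regression-to-the-mean figures rest on assumed values, and they concern a mean-change test that the plan does not clearly state. For the dose slope, drift does little numerical harm. With two homes, any contrast is also only weakly randomised.

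It does not remove the point. Fixing the outcome as change from baseline to after the intervention, in all analyses, conflicts with the per-visit reading; no control-period change or resident-level effect is defined. Even on that reading the predictor is received dose, not assigned condition. Diagnostics chosen after the data are seen supply no contrast. Agitation is the lead outcome of Aim 1, with a stated hypothesis and a power calculation, so the pilot label does not excuse the gap.

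**Conclusion.** The concern holds and must be fixed. As written, the Aim 1 analysis does not test SABL against the control period. Followed literally, it answers a different, non-randomised question and leaves all 72 control-period CMAI scores without a use. This follows from the text and the calendar alone and needs no assumed value.

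The secondary consequences are conditional. The 0.12 to 0.30 SD gap between homes depends on the assumed drift and on the first two readings of *post-intervention*. The regression-to-the-mean figures depend on the screening score being the baseline. Inflation of the dose-slope error rate is small, at 5 to 8%.

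**What to change.** In section 8.3 and the SAP:

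- Define *post-intervention* by visit week for each home.
- Make the primary analysis a mixed model of the CMAI score at each visit (likewise NPI-NH and ARS), with a resident random effect, fixed effects for home and visit week, and condition as the primary term. The contrast is SABL visits against control visits: NH A weeks 3 and 5 against 9 and 11; NH B weeks 9 and 11 against 3 and 5.
- As a secondary analysis, compare post-intervention with post-control at weeks 7 and 13.
- Keep the received-dose model as a secondary, per-visit analysis.
- Report change from baseline descriptively, and say whether the baseline CMAI is the screening score.
- State the limits: with one home per sequence, home-by-period effects cannot be separated from treatment, and the contrast assumes no carryover beyond the two-week washout.

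Section 7.2.2 covers visits 2 to 6 only. It needs one line to match the seven visits in section 7.2, since week 13 is visit 7.

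The cost is wording: Table 1 already schedules every assessment. If d = 0.53 is the standardised SABL-minus-control difference, a period-adjusted contrast with 36 completers (34 degrees of freedom) has power 0.871 two-sided or 0.929 one-sided, ignoring any home-by-period effect. The sidedness of the test should therefore be stated as well.

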- 1) Data extraction from CMS Nursing Home Compare Website (<https://www.medicare.gov/care-compare/>): Data on facility characteristics, including number of certified beds, ownership, quality rating, participation in Medicaid, staffing, COVID-related data is publicly available and can be accessed through the link provided above.
- 2) Chart reviews: Data on resident characteristics, including age, race, sex, diagnoses, level of cognitive impairment, current medication use, current listed comorbidity and physical function, BPSD in the past two weeks, pain in the past two weeks, current vision status, current hearing status, and other clinical conditions.
- 3) Surveys based on staff caregivers' reports: The surveys will be conducted on paper and in-person with researcher administering the survey to the staff caregiver for proxy report of residents' dementia stage, agitation, other BPSD, affect, and side effects.
- 4) Personal light monitor, LYS button, placed on individual resident participants to measure lighting intensity (lux) and CS levels participants receive.

There will be seven visits for data collection throughout the 13-week of the study: baseline visit (week 1) and six follow-up visits, every other week (weeks 3, 5, 7, 9, 11, 13). The procedures for each visit are as follows:

Baseline visit: Procedures 1 through 4.

Follow-up visits: Procedures 3 and 4.

For the procedure 4, the light monitor will be worn 7 days a week during the data collection weeks (week 1, 3, 5, 7, 9, 11, & 13).

Aim 2: We will evaluate the fidelity of SABL delivery by measuring lighting intensity (lux) and CS levels.

Data collection procedures will include the following:

- 1) on-site manual light measurements
- 2) personal light monitor, LYS button, placed on individual resident participants (same as the procedure 4 in aim 1).

The procedures will be conducted primarily on site at the nursing home facilities.

The procedure 1 will be conducted twice a week throughout the 13-week study period.

For the procedure 2, as mentioned in aim 1, the light monitor will be worn 7 days a week during the data collection weeks (week 1, 3, 5, 7, 9, 11, & 13).

Aim 3: Staff and Administrators

Data collection methods include the following:

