7.3 Duration of Participation

Describe how long subjects will be involved in this research study. Include the number of sessions and the duration of each session - consider the total number of minutes, hours, days, months, years, etc.

Aims 1 and 2: Residents

The study lasts 13 weeks with baseline data collection: one week for baseline, four weeks for intervention (SABL), two weeks for post intervention/washout period, four weeks for control, and two weeks for post control. The baseline survey of the residents regarding cognitive function and agitation may take 10 minutes to complete.

Aim 3: Staff and administrators 1-2 visits for a total of 1-2 hours. The surveys will take approximately 10-15 minutes to complete, and the interview will take about 1 hour.

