7.4.3 Method for Assigning Subject to Treatment Groups

Describe the randomization process and how the associated treatment assignment will be made.

The study design is a crossover, cluster randomized controlled trial. We plan to conduct the study in two nursing homes. The study procedures include five phases over 13 weeks (Table). The two NHs will be randomly assigned into different sequences for intervention and control. Otherwise, the same study procedures will be conducted simultaneously at the two nursing homes. During the daytime, participants will be guided and encouraged to spend time in the designated areas in the dining room and activity room for their meals and daily activities.

Table. Intervention testing procedures and timeline.

Week	1	2	3	4	5	6	7	8	9	10	11	12	13
------	---	---	---	---	---	---	---	---	---	----	----	----	----

Study phases	NH A	Baseline	Intervention		Post intervention/washout		Control			Post control	
	NH B		Control		Post control/washout		Intervention			Post intervention	
Lighting	Usual light		I: SABL C: Usual light		Usual light		C: Usual light I: SABL			Usual light	
Data collection	Baseline, L&E		L&E	L&E		L&E		L&E	L&E		L&E

L=lighting measured via individual light monitor, E=effect outcomes (e.g., agitation, BPSD, affect, and sleep) and adverse effects

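### The Aim 1 change from the single week-1 baseline covers 4–6 weeks in one home and 10–12 weeks in the other, and nothing written in the plan removes the difference

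*Protocol*

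**What the plan says.** Protocol 8.3 (Aim 1) takes "Baseline to post-intervention changes in participants" on the CMAI, NPI-NH and ARS as the outcome for every later analysis. The SAP repeats the sentence. Neither says which visit counts as post-intervention, and neither names a second baseline.

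Protocol 7.2 schedules a "baseline visit (week 1) and six follow-up visits, every other week (weeks 3, 5, 7, 9, 11, 13". Protocol 7.3 gives the phase lengths as "one week for baseline, four weeks for intervention (SABL), two weeks for post intervention/washout period, four weeks for control", followed by two weeks after control. On allocation, 7.4.3 says: "The two NHs will be randomly assigned into different sequences for intervention and control". It adds: "Otherwise, the same study procedures will be conducted simultaneously at the two nursing homes". In Table 1, NH A has SABL first and NH B has control first.

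On the model, 8.3 says: "We will use the daytime and nighttime average of lighting dosages (lux and CS) from the personal light monitors as the independent variable". It adjusts for clustering at facility level and adds that "each participant will serve as their own control, which allows minimal use of control variables". The hypothesis in 7.1 compares agitation during and after SABL with both the baseline and the control periods. No period term, sequence term or SABL-minus-control contrast appears in 8.3 or the SAP.

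**The concern.** One outcome label covers two different quantities. In NH A, week 1 is the reading immediately before SABL. In NH B, SABL starts only after four control weeks and two washout weeks, so a change measured from week 1 also takes in any effect of the sham installation described in 7.4.25 and six more weeks of whatever else moves the scores, such as disease course, staffing, season or familiarity with the study.

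Because each sequence is a single home, interval length and home are the same variable. A facility-level adjustment with two facilities cannot tell six weeks of time trend from any other difference between the homes. At stake is whether a SABL change pooled over the homes describes one quantity, and whether a difference between the homes' changes can be interpreted at all.

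**Working it through.** **1. Timeline.** The phase lengths in 7.3 sum to 1 + 4 + 2 + 4 + 2 = 13 weeks, which reproduces the stated duration. The phases are week 1 (baseline), weeks 2–5, 6–7 (washout), 8–11 and 12–13.

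**2. Intervals.** Span = assessment week minus baseline week. Both readings of post-intervention are shown: the last visit on SABL, and the visit in the post-intervention phase.

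| Home | SABL weeks | Last visit before SABL | Span from week 1 | Span from last visit before SABL |
|---|---|---|---|---|
| NH A | 2–5 | week 1 | 5 − 1 = 4; 7 − 1 = 6 | 4; 6 |
| NH B | 8–11 | week 7 | 11 − 1 = 10; 13 − 1 = 12 | 11 − 7 = 4; 13 − 7 = 6 |

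On either reading the excess in NH B is 6 weeks: the 4 control weeks plus the 2 washout weeks. NH B's week 7 is under usual light with no earlier SABL, and 7.2 already schedules outcome measurement then.

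**3. Illustrative size.** The documents give no time trend, so assume linear drift of g SD per week, common to both homes. NH B's change carries 6g more than NH A's. With 20 residents per home, a simple mean over the homes is shifted by 6g/2 = 3g.
- g = 0.01: 0.03 SD, and 0.03/0.53 = 6% of the planned effect size (d = 0.53, protocol 8.2).
- g = 0.05: 0.15 SD, and 0.15/0.53 = 28%.

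**4. What a week-7 start in NH B removes.** The average span falls from (4 + 10)/2 = 7 weeks to 4, or from (6 + 12)/2 = 9 weeks to 6. That removes 3/7 = 43% or 3/9 = 33% of the drift in a pooled mean change. The remaining 4–6 weeks stay in both homes.

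**5. The contrast with control.** With a shared week-1 baseline, (SABL − week 1) − (control − week 1) = SABL − control, so the baseline cancels. At end of phase the drift is 4g − 10g = −6g in NH A and 10g − 4g = +6g in NH B. The equally weighted mean is 0.

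**6. Separate period baselines in that contrast.** Assume equal variances and equal correlation ρ between all visits. SALB-minus-control with a shared baseline has variance 2σ²(1 − ρ). Subtracting a different baseline in each phase gives 4σ²(1 − ρ), so the SD rises by √2, or 41%. NH A's week 7 also follows SABL. If half of d = 0.53 persisted at that visit and then faded (assumption), NH A's control change would be off by 0.265 SD and the pooled contrast inflated by 0.265/2 ≈ 0.13 SD.

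**The case against.** The strongest reply is that the crossover is meant to be read within person. The own-control sentence in 8.3 and the hypothesis in 7.1 point to a SABL-versus-control comparison, in which the shared baseline cancels and common linear drift averages to zero (step 5). This is right for that comparison, but the comparison is not written: the only outcome defined is the change from baseline. The hypothesis also compares SABL with baseline itself, and there the mismatch does not cancel.

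Second, the planned model regresses change on light dose with adjustment for facility. Drift common to all residents of NH B shifts that home's level; it does not bias the dose slope within the home, and a facility intercept absorbs at least part of it. This stands. A reader might take 0.03–0.15 SD, or 6–28% of d, as the bias of the planned analysis. The documents do not support that, because the figure belongs to a simple pooled mean and the drift rate is assumed.

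Third, a reader might infer that NH B's change is contaminated by another treatment. It is not: control is usual light with non-SABL bulbs, so the extra weeks add elapsed time and any sham effect. Seasonal light is also partly covered, since monitors record the light received and daylight exposure is an exploratory covariate.

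Fourth, it is tempting to give every phase its own baseline, with week 7 for NH A's control phase. Step 6 shows why that should not be primary: the visit may carry SABL effect, and separate baselines cost precision.

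Finally, moving NH B to week 7 has its own cost. Residents are selected on high CMAI before week 1, so regression to the mean then enters NH A's SABL change but much less NH B's. This stands as a downside.

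**Conclusion.** The point holds as a gap in specification. As written, the SABL change covers 4–6 weeks in NH A and 10–12 in NH B. The six-week difference follows from the protocol's own schedule, is inseparable from home, and is not removed by anything in 8.3 or the SAP. Its effect on the estimate cannot be derived from the documents; the 0.03–0.15 SD in step 3 rests on an assumed drift and on a simple pooled mean.

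Two limits apply to the remedy. Equal intervals still contain 4–6 weeks of drift, so a pre-post change cannot attribute improvement to SABL alone. The SABL-minus-control contrast removes drift only if it is common to both homes and they are weighted equally. A home-specific trend stays confounded with one home per sequence, and carryover into NH A's control phase is not removed.

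**What to change.** In protocol 8.3 and the SAP:

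- For any baseline-to-post-SABL change, define baseline as the last visit before SABL starts: week 1 in NH A and week 7 in NH B.
- Name the post-intervention visit, at the same position in both homes: weeks 5 and 11, or weeks 7 and 13.
- For the comparison with control, specify the within-person SABL-minus-control contrast with a period term, using the shared week-1 baseline or none.
- Do not use NH A's week 7 as the primary baseline for its control phase.
- Report the SABL change in NH B from week 1 as a sensitivity analysis, and state that regression to the mean after selection on CMAI affects the two homes' SABL changes unequally under the main definition.

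The cost is wording, one model term and one sensitivity analysis. Week-7 outcomes are already scheduled in both homes, so no visits, measurements or participants are added.
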